## 4. INVESTIGATIONAL PLAN

### 4.1 Overall Study Design

The Carolinas Cardiogenic Shock Initiative is a clinical pathway and process improvement protocol already agreed upon by participating sites, to improve care by using a standardized algorithm to treat patients with AMI and CS. This prospective registry will capture data from this protocol as a multi-site research project in parallel with this standardized non-research clinic workflow protocol. Participating providers will follow the clinical protocol as standard of care for AMICS patients, as clinically appropriate. Patients who have been admitted and diagnosed with AMICS and meet all eligibility criteria will have their data entered in this registry.

All eligible patients will be entered into the registry and follow-up via the EMR and/or SSDI will occur at 30 days and one year to assess mortality. No additional provider appointments or further testing will be required as a part of this Registry, other than what each provider feels is medically necessary and indicated as a part of the patients' care plan.

Treatment decisions and timing will follow an approved clinical protocol and algorithm (see Appendix A) based on shock severity classification. The research team at each site will capture data generated during standard of care lab tests and clinical procedures, as well as data collected during clinical visits from eligible patients. Our target accrual is approximately 672 patients, cumulative across all participating sites.

Many of the patient specific outcomes and variables of interest for this study, are already submitted to the National Cardiovascular Data Registry (NCDR). Some additional data elements, as described in Appendix C, will also be captured. There are no benefits in participation other than the scientific knowledge gained, and the only alternative to participation is not participating.

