#### 4.4.2.1. Hypothesis 1.

##### Approach

To evaluate this hypothesis, we will use a discrete time survival analysis (DTSA) within the structural equation modeling (SEM) framework (Muthén & Masyn, 2005; Raykov, Gorelick, Zajacova, & Marcoulides, 2017). This approach offers substantively important extensions to conventional DTSA models (e.g., logistic regression) that more accurately reflects the complexity and interconnectedness of survival (i.e., event history modeling) processes (Masyn, 2014). This more general approach includes the ability to model unobserved population heterogeneity (frailty) in the event history process, latent variable predictors of event history (e.g., health-related quality of life) including possible mediators and moderators, recurring events, competing risks, parallel and sequential growth processes (i.e., between-person variability in within-person change over time), onset-to-growth models, parallel event history processes, measurement error on event occurrence, hazard risk set matching, handling multilevel data structures, and time-varying covariate effects (non-proportional hazard) among other advantages (Masyn, 2013, 2014). Figure 1 presents an exemplary DTSA within the context of SEM (simplified for ease of presentation). In this example, three binary indicators (1, event occurred; 0, event not occurred) corresponding to the  $j = 3$  proposed measurement occasions ( $e_j$ ). In this analysis the hazard probability for a given measurement occasion will be defined as the probability of mortality in that occasion, provided that patient is alive. The hazard probability will then be related to time-varying ( $w_j$ ) and time-invariant ( $x$ ) covariates through a logit link function to parameterize the effect of a particular covariate on the log hazard odds of mortality during a given time interval. We will then describe covariate effects in terms of a hazard odds ratio (hOR). For example, if clinical protocol is coded 1 for typical and 0 for being based on a shock severity score, were estimated to have a hOR of 2.0 at 30 days, we would note that the odds of mortality at 30 days for those without a shock severity protocol was twice the odds of mortality at 30 days for those with a shock severity protocol. This model can be written as:  $logit(Pr(e_j = 1)) = \alpha_j + \beta_j x + \gamma_j w_j$ , where  $\alpha_j$  is the log hazard odds (with all covariates set to 0),  $\beta_j$  is the difference in the log hazard odds and  $exp(\beta_j)$  is the hazard odds ratio (hOR) for a positive one unit difference in  $x$  (controlling for covariates  $w_j$ ), and  $\gamma_j$  represents a time-varying covariate effect for the difference in log hazard odds. The assessment of non-inferiority will be performed by comparing hazard odds ratio confidence intervals to the non-inferiority margin (Althunian, Boer, Groenwold, & Klungel, 2017). Specifically, since lower is better, non-inferiority will be concluded when the actual hazard ratio is less than the clinically acceptable ratio of 1.2.

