
### *Power*

With respect to the 30-day primary end point of death, we estimated that an overall sample size of 672 patients would provide 80% power (at a one-sided alpha level of 0.025) to show the noninferiority of a standardized clinical protocol that selects patients for MCS based on shock severity to a standard clinical protocol that does not differentiate based on shock severity assuming the proportion of subjects observed with the event (death) during the study is 39.7% for the control group and 41.3% for the treatment group (Thiele et al., 2005; Thiele et al., 2013). The power was computed for the case when the actual treatment group proportion is 31%. The test statistic used is the one-sided Z test (unpooled).

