### *Potential problems and alternatives*

The issue of multiple testing that is involved in evaluating the p-values associated with a large set of covariates, is not addressed through the use of SEM. To address this concern, we will use the Benjamini–Hochberg (BH) procedure that is based on the false discovery rate concept, and has been shown to be more powerful than conventional multiple testing procedures (Benjamini & Hochberg, 1995; Benjamini & Yekutieli, 2001; Raykov, Lichtenberg, & Paulson, 2012). The inclusion of time-dependent covariates introduces reciprocal causation (Singer & Willett, 2003). We will address this issue by modeling covariate effects with a time-lag (Brown, 2012; Little, 2013). Model comparisons based on the Wald statistic test (dividing a parameter estimate by its standard error), may be influenced by non-normal concentration distributions (Little, 2013). To address this, we will use the adjusted likelihood ratio test statistic (i.e., Chi-Square Difference Test) using the log likelihood values and scaling correction factors obtained with the “MLR” estimator in Mplus, the default maximum likelihood estimator for binary and ordinal outcomes (Wang & Wang, 2012). In the event of unforeseen problems related to the proposed models, we will simplify our approach by modeling single-occurrence events in discrete-time with observed predictors using a multivariate logistic regression to model conditional model-estimated hazard probabilities and corresponding survival probabilities (Masyn, 2014; Muthén & Masyn, 2005). In this case, noninferiority will be calculated with the use of the Com–Nougue approach to estimating the z statistic for the Kaplan–Meier failure rates, with standard errors estimated by means of Greenwood’s formula (Com-Nougue, Rodary, & Patte, 1993).

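### The Hypothesis 1 non-inferiority ratio is conditional on time-varying covariates that are not restricted to values from before the protocol acts, so it may not be the total protocol effect

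*Protocol*

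**What the plan says.** Section 4.4.2.1 (Approach) gives the model logit(Pr(e_j = 1)) = α_j + β_j x + γ_j w_j. Here x is time-invariant and w_j time-varying, and the worked example uses clinical protocol as the covariate whose ratio is interpreted. The hazard odds ratio exp(β_j) is defined with w_j controlled for, and γ_j "represents a time-varying covariate effect for the difference in log hazard odds". Non-inferiority is judged by setting the confidence interval of this ratio against 1.2.

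Section 4.4.2.1 (Potential problems and alternatives) recognises one difficulty: "The inclusion of time-dependent covariates introduces reciprocal causation". The remedy follows: "We will address this issue by modeling covariate effects with a time-lag". The length of the lag is not given.

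Three other places matter:
- Section 4.4.1 fixes the occasions as baseline, one month and one year.
- Section 4.4.2 (Missing Data) also provides for time-varying covariates, so they are intended.
- Section 1.1 and the goals in Section 4.4.2 ask whether the protocol is non-inferior on mortality. Section 1.1 names both one month and one year, and Section 4.1.1 makes 30-day all-cause mortality primary.

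**The concern.** The hypothesis is about the total effect of following one clinical protocol rather than another. The protocol acts during the index admission, through the selection and timing of MCS. A covariate value recorded after that may be a consequence of the protocol. Holding it fixed removes whatever part of the effect passes through it, and what remains is a direct effect. It also conditions on a variable that may share unmeasured causes with death.

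A lag ensures that the covariate precedes the interval in which death is counted. It does not ensure that the covariate precedes the treatment decision. At stake is whether the ratio compared with 1.2 answers the question that Hypothesis 1 asks.

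**Working it through.** **1. The plan's own figure.** Section 4.4.2.1 (Power) states that "an overall sample size of 672 patients would provide 80% power" at one-sided alpha 0.025. It takes "39.7% for the control group and 41.3% for the treatment group" and adds: "The power was computed for the case when the actual treatment group proportion is 31" (per cent). The test is an unpooled Z test. Allocation is not stated, so 1:1 is assumed.

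n per group = [0.397×0.603 + 0.31×0.69] × (1.96 + 0.8416)² / (0.016 + 0.087)² = 0.4533 × 7.849 / 0.01061 = 335.4, rounded up to 336. The total is 672, which reproduces. The test has no covariates, so this figure says nothing for or against the adjusted model.

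**2. What a lag does, occasion by occasion.**
- One-occasion lag, 30-day hazard: w_j is the baseline value. This is safe if baseline precedes the MCS decision.
- One-occasion lag, one-year hazard: w_j is the one-month value, which is post-protocol.
- Any shorter lag: the 30-day hazard can also be adjusted for post-protocol values.

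**3. Size when the protocol is harmful at the margin.** Let a share f of the total log odds ratio pass through w_j. The adjusted model then targets (1 − f) × log(OR). The documents give no f, so the assumed range is 25% to 75%. Non-inferiority is concluded when the upper 97.5% limit is below 1.2:

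P = Φ{[log 1.2 − (1 − f) log OR] / SE − 1.96}

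A true odds ratio of 1.2 on 39.7% gives 44.1%. With 336 per group, SE = √[1/(336×0.397×0.603) + 1/(336×0.4414×0.5586)] = √(0.01243 + 0.01207) = 0.1565, and log 1.2 = 0.1823.

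- f = 0: Φ(−1.96) = 2.5%
- f = 25%: Φ(0.291 − 1.96) = 4.8%
- f = 50%: Φ(0.582 − 1.96) = 8.4%
- f = 75%: Φ(0.874 − 1.96) = 13.9%

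**4. Size under the planned benefit.** 31% against 39.7% is an odds ratio of 0.682, with log −0.382. SE = √(0.01391 + 0.01243) = 0.1623.

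- f = 0: Φ(3.478 − 1.96) = 93.5%
- f = 25%: 82.4%
- f = 50%: 63.3%
- f = 75%: 40.2%

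The starting value is 93.5% and not 80% because the 1.2 margin is wider than the bound used for power (41.3% against 39.7%, odds ratio 1.07).

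**5. Simulation check.** The assumptions are a binary mediator with 40% prevalence in control and a conditional log odds ratio of 1.2, with 4,000 runs per scenario. At f = 25%, 50% and 75% the adjusted model concluded non-inferiority in 4.4%, 7.0% and 12.8% of runs at the margin, and in 82.6%, 61.5% and 37.9% under benefit. With no mediation at the margin, the adjusted and unadjusted rates were 2.0% and 2.3%. The inflation is therefore not an artefact of odds ratios changing when a covariate is added.

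All ratios here are new protocol against typical protocol. The worked example in the Approach codes the groups the other way round.

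**The case against.** The strongest reply is that the protocol never names w_j and never says that it is measured after the protocol has acted. The model figure is offered as a simplified example. Section 4.4.2 speaks of covariates with time-varying effects, and baseline covariates can have such effects. A covariate list is commonly left to the SAP. On a one-occasion lag the primary 30-day hazard uses baseline values, which leaves only the secondary one-year outcome exposed. Even there, the only items that Section 4.3 dates to one and twelve months are survival.

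Much of this stands. Adjustment for post-protocol values is permitted, not certain, and at 30 days it depends on an unstated lag. It does not remove the point. The Approach calls the covariates themselves time-varying, and the lag would be unnecessary if they were all baseline values. The list in Section 4.3 is only partial and includes post-procedure information. The objection is to the decision equation and the remedy that the protocol does state, not to a missing list.

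A reader might also infer that the adjustment always favours non-inferiority, or that a clearly inferior protocol would routinely pass. The documents support neither. The bias favours non-inferiority when the protocol is harmful and w_j carries that harm. Under the protocol's own assumed benefit it works the other way, and bias from shared causes can go in either direction. The decision also rests on a confidence limit. An adjusted point estimate below 1.2 is not enough, and even with 75% of the harm mediated the error rate at the margin is about 14%.

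**Conclusion.** The point holds in a limited form. As written, the ratio that decides Hypothesis 1 is conditional on time-varying covariates with no pre-treatment restriction, and the lag does not address mediation. The one-year contrast is exposed on a one-occasion lag. The 30-day primary contrast is not clearly protected because the lag length is unstated.

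If w_j carries 25-75% of the effect, false non-inferiority at a true odds ratio of 1.2 is about 5-14% instead of 2.5%. Under the planned benefit the chance of success falls from 93.5% to 82-40%. These figures assume 1:1 allocation, a single interval and the 30-day mortality rates, the only ones given. The one-year hazard would be estimated among 30-day survivors, so for that contrast the figures show the mechanism and are not a forecast. The mediated share is an assumption.

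**What to change.** State in Section 4.4.2.1 that the 30-day and one-year non-inferiority decisions rest on a model whose covariates are all fixed before the MCS decision. Effects of those covariates may still differ between intervals. Label any model with time-varying w_j exploratory, and state its lag length. Apply the same restriction to the fallback logistic regression.

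The cost is wording only. Section 4.3 already collects demographics, medical history and admission characteristics. The 672 is unaffected, because it comes from an unadjusted test.

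### The sentence that sets the 1.2 non-inferiority margin calls it a hazard ratio, although the model and the planned comparison use a hazard odds ratio; at about 40% mortality the two differ

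*Protocol*

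**What the plan says.** Protocol section 4.4.2.1 (Approach) specifies a discrete-time survival model with a logit link. It defines the hazard as a probability: "the hazard probability for a given measurement occasion will be defined as the probability of mortality in that occasion, provided that patient is alive". The exponentiated coefficient is named as the hazard odds ratio (hOR), and covariate effects are to be described on that scale.

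The decision rule follows in two sentences:
- The first sets the comparison and gives no number: "The assessment of non-inferiority will be performed by comparing hazard odds ratio confidence intervals to the non-inferiority margin".
- The second gives the number and changes the term: "non-inferiority will be concluded when the actual hazard ratio is less than the clinically acceptable ratio of 1.2".

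The figure 1.2 appears nowhere else. The protocol does not say that the two terms are interchangeable, and it does not convert 1.2 to a mortality rate.

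The Power paragraph of the same section works on a different scale, a difference of proportions with an unpooled Z test. It assumes 39.7% deaths in the control group and 41.3% in the treatment group, states that "an overall sample size of 672 patients would provide 80% power" ("at a one-sided alpha level of 0.025"), and adds that "The power was computed for the case when the actual treatment group proportion is 31"%. It does not mention 1.2. The primary outcome is 30-day all-cause mortality (section 4.1.1).

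**The concern.** An odds ratio and a hazard ratio nearly coincide only when events are rare. Here about four in ten control patients are expected to die in the first interval, so the same 1.2 permits different numbers of deaths on the two scales. This is the threshold for the primary hypothesis, on mortality. A rule whose two sentences name different effect measures leaves room to argue, once the data are known, about which one was meant. The absolute excess mortality that 1.2 accepts is also not stated, so a reader cannot settle the matter from the clinical side.

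**Working it through.** **Inputs.** From section 4.4.2.1: margin 1.2; control mortality 39.7%; treatment limit 41.3%; true treatment mortality 31% for power; total 672; one-sided alpha 0.025; power 80%. Equal groups of 336 are my assumption, because the protocol gives only the total.

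**1. The plan's own figure.** Take 41.3% as the non-inferiority limit, so the margin on the difference scale is 0.413 − 0.397 = 0.016. The true difference in favour of the severity-based protocol is 0.397 − 0.31 = 0.087.

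n per group = (1.960 + 0.842)² × (0.397×0.603 + 0.31×0.69) / (0.016 + 0.087)² = 7.849 × 0.4533 / 0.010609 = 335.4, rounded up to 336.

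The total is 672, as stated, and power at 336 per group is 80.1%. So 41.3% acts as the limit behind the sample size.

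**2. What 1.2 allows at 39.7% control mortality.** Control odds = 0.397/0.603 = 0.6584.

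| Meaning of 1.2 | Formula | Deaths allowed | Excess over 39.7% | As odds ratio |
|---|---|---|---|---|
| Hazard odds ratio | 1.2×0.6584 / (1 + 1.2×0.6584) | 44.1% | +4.4 points | 1.20 |
| Continuous-time hazard ratio, proportional hazards | 1 − 0.603^1.2 | 45.5% | +5.8 points | 1.27 |
| Ratio of the discrete hazards (interval probabilities) | 1.2 × 0.397 | 47.6% | +7.9 points | 1.38 |

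The first two differ by 1.4 points, and the first and third by 3.5 points.

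**3. The sample-size limit on the same scale.** The odds ratio for 41.3% against 39.7% is (0.413/0.587)/0.6584 = 1.07, an excess of 1.6 points. This matches none of the three readings of 1.2.

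**4. Power, log odds ratio scale, 336 per group.** Power = Φ[(ln margin − ln true OR)/SE − 1.96].

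- Equal true mortality of 39.7%: SE = √(2/(336×0.397×0.603)) = 0.1577.
- True treatment mortality of 31%: true OR = (0.31/0.69)/0.6584 = 0.682, and SE = √(1/(336×0.397×0.603) + 1/(336×0.31×0.69)) = 0.1623.

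| True treatment mortality | Margin 1.20 | Margin 1.27 |
|---|---|---|
| 39.7% (equal) | 21% | 33% |
| 31% (the plan's case) | 94% | 97% |

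**The case against.** The section largely settles the scale itself. It specifies a logit link, names the exponentiated coefficient as the hOR, and explains a 30-day hOR in words. The decision sentence is introduced as a specific form of the hOR comparison just stated. Mortality is recorded only at baseline, one month and one year (section 4.4.1), and no continuous-time hazard ratio is proposed as an effect measure. On this view the term is loose shorthand for hOR. I accept that as the likely intent.

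Three stronger readings therefore fail:
- **That 1.2 is itself given on both scales.** It is not. The hOR sentence speaks only of the margin; the number stands once, beside the words hazard ratio.
- **That the same data will both pass and fail, or that more deaths are accepted than intended.** The planned model yields an hOR to be compared with 1.2. An upper hOR limit between 1.20 and 1.27 (or 1.38) changes the conclusion only if another scale is adopted. The 1.27 figure rests on a quantity that the protocol does not propose.
- **That the wording leaves the study with 21% to 33% power.** Those figures assume equal true mortality. In the plan's own case of 31% treatment mortality, power is about 94% or 97%.

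What stands is that the sentence fixing the primary threshold names a quantity that the model does not estimate, and nothing in the text declares the terms equivalent.

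**Conclusion.** The point holds as an inconsistency in the primary decision rule that should be corrected. It does not show that the planned analysis uses the wrong threshold. At 39.7% control mortality the scales are not interchangeable: the permitted mortality is 44.1%, 45.5% or 47.6%. The smallest gap, 1.4 points, is nearly as large as the whole 1.6-point limit behind the sample size.

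The more consequential conflict appears once 1.2 is put in absolute terms. Even on the likely hOR reading it accepts +4.4 points, against +1.6 points in the Power paragraph.

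The conversions take 39.7% as the control group's 30-day hazard and treat the ratio as unadjusted. The 45.5% also needs proportional hazards in continuous time. A covariate-adjusted hOR of 1.2 would not correspond exactly to 44.1%, which is a further reason to report a standardised risk difference.

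**What to change.** 1. In the decision sentence of section 4.4.2.1, replace the term hazard ratio with *the 30-day hazard odds ratio (severity-based versus standard protocol)* and keep 1.2 on that scale. The direction needs stating because the worked example in that section codes the typical protocol as 1, which runs opposite to a rule in which lower is better.
2. Give the absolute equivalent beside it: 44.1% against 39.7%, or +4.4 points.
3. Do not use 1.27 unless the sponsor confirms that a continuous-time hazard ratio was intended.
4. Reconcile this margin with the 41.3% limit in the Power paragraph. Inserting 44.1% alone would leave the decision margin and the sample size in open contradiction.
5. Report the covariate-standardised 30-day risk difference beside the hOR.
6. If power is restated, give the allocation assumption and both scenarios, equal mortality and 31%.

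The wording change is one sentence and needs no new data. The reconciliation also requires the Power paragraph to be revised and the sponsor to decide which margin is meant.

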
### *Power*

With respect to the 30-day primary end point of death, we estimated that an overall sample size of 672 patients would provide 80% power (at a one-sided alpha level of 0.025) to show the noninferiority of a standardized clinical protocol that selects patients for MCS based on shock severity to a standard clinical protocol that does not differentiate based on shock severity assuming the proportion of subjects observed with the event (death) during the study is 39.7% for the control group and 41.3% for the treatment group (Thiele et al., 2005; Thiele et al., 2013). The power was computed for the case when the actual treatment group proportion is 31%. The test statistic used is the one-sided Z test (unpooled).

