### 4.4 Statistical Analysis

**4.4.1. Exploratory analysis.** Variable distributions will be examined using summary measures, tables, and graphics, such as histograms and scatter plots, where appropriate. Variables will initially be used as they were obtained; however, transformation may be

necessary or prove more informative. For example, continuous variables may be categorized, using common category boundaries found in the literature or based on percentiles of the variable distribution, in order to stratify the data. Student's t-test or the Wilcoxon rank-sum and chi-square statistics will be used to examine simple associations. For event history outcomes, we will primarily rely on survival analysis (i.e., event history modeling) to investigate if and when the event has occurred (Singer & Willett, 1993). For this study, the time scale for mortality will be recorded in discrete time intervals (i.e., baseline, one month, one year); therefore, the underlying continuous time-to-event process will be modeled using discrete time.

A major consideration will be the nested organization of the data. Patients (level-1) are nested within sites (level-2). When hierarchical data are analyzed without regard to the interdependence of the data type-I error rates are inflated (aggregation) or deflated (disaggregation) resulting in incorrect significance tests and invalid conclusions (Hox, 2002). While multilevel modeling methods explicitly account for the nested structure of data, this approach is not feasible because we do not have sufficient number of sites to treat these effects as random (Hox & Roberts, 2010; Roberts, Monaco, Stovall, & Foster, 2011). Therefore, each site will be evaluated for differences in multiple group analyses. If the site differences are trivial, we will collapse the data across sites (Little, 2013). Non-trivial differences will require a grouping variable for site in subsequent analyses.

**4.4.2. Analytic strategy.** Insights gained from the exploratory data analysis will then be used to fit appropriate statistical models to the data. Within the context of survival analyses, we will begin by modeling the unconditional model (no covariates) in order to establish a baseline model. Next, we will add covariates with time-varying (nonproportional hazard odds) effects. Using model constraints, we will then fit a proportional hazard odds model and compare. Finally, we will probe for hypothesized effects.

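### The 80% power at 672 assumes independent patients although the pathway is adopted by sites, and section 4.4.1 gives the wrong direction of the clustering error for a site-level exposure

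*Protocol*

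**What the plan says.** Section 4.4.1 opens its treatment of site with "A major consideration will be the nested organization of the data". It warns that if the nesting is ignored, "type-I error rates are inflated (aggregation) or deflated (disaggregation) resulting in incorrect significance tests and invalid conclusions". It then rules out random site effects because there are too few sites. Data are to be pooled if site differences look trivial; otherwise a site grouping variable is added.

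The Power paragraph under Hypothesis 1 gives "an overall sample size of 672 patients would provide 80% power (at a one-sided alpha level of 0.025"). The death rate "is 39.7% for the control group and 41.3% for the treatment group", and "The power was computed for the case when the actual treatment group proportion is 31" per cent. The test is an unpooled one-sided Z test on two proportions. No number of sites, ICC or design effect appears.

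Section 4.1 describes the intervention as a "clinical pathway and process improvement protocol already agreed upon by participating sites", followed by providers there as standard of care. The target of 672 is a total over participating sites. No section says where patients managed without severity-based selection come from.

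**The concern.** The plan recognises clustering and then sizes the study as if there were none. That matters most when the exposure is a property of the site, which is how section 4.1 describes the pathway. Patients at one site share operators, referral patterns and case mix. If a whole site falls in one group, those shared features do not average out between the groups.

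The sentence in 4.4.1 points the wrong way for that case. Treating patients as independent when the exposure is set by site (disaggregation) overstates the effective sample size and inflates type I error. Deflation can occur for an exposure that varies within site, but the sentence carries no such limit. At stake are the stated power and, in a non-inferiority comparison of mortality, an interval that may be too narrow when it is set against the margin.

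**Working it through.** **Inputs from the Power paragraph.** Control 39.7%, limit for the treatment group 41.3%, true treatment rate 31%, one-sided alpha 0.025, total 672. Allocation is not stated; 336 per group is assumed.

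**The plan's own figure.**
- Variance sum: 0.397×0.603 + 0.31×0.69 = 0.4533.
- Patients per group: 0.4533×(1.960+0.842)²/(0.413−0.31)² = 335.4, so 336 per group and 672 in total.
- SE = √(0.4533/336) = 0.0367.
- Standardised distance: 0.103/0.0367 = 2.804 (unrounded SE).
- Power = Φ(2.804−1.960) = 80.07%.

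The arithmetic is right, with a design effect of 1.

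**The same rates against the margin in the Approach paragraph.** That paragraph compares a hazard odds ratio with 1.2. The 41.3% limit corresponds to (0.413/0.587)/(0.397/0.603) = 1.07, so the two are different tests. Taking the ratio as severity-based over control:
- Log odds ratio: ln(0.31/0.69) − ln(0.397/0.603) = −0.382.
- SE = √[1/(336×0.397×0.603) + 1/(336×0.31×0.69)] = 0.1623.
- Standardised distance: (0.182+0.382)/0.1623 = 3.478.
- Power = Φ(3.478−1.960) = 93.5%.

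**Clustering, if each site lies wholly in one group.** Site number k and ICC are assumptions, and sites are taken as equal in size.
- m = 672/k, and D = 1+(m−1)×ICC.
- Power with a correct SE: Φ(2.804/√D − 1.960) at the 41.3% limit, or Φ(3.478/√D − 1.960) at 1.2.
- One-sided error if clustering is ignored: 1−Φ(1.960/√D).

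| Sites (ICC 0.01) | m | D | Power, 41.3% limit | Power, margin 1.2 | Error if ignored |
|---|---|---|---|---|---|
| 6 | 112 | 2.11 | 49% | 67% | 8.9% |
| 10 | 67.2 | 1.66 | 58.5% | 77% | 6.4% |
| 20 | 33.6 | 1.33 | 68% | 86% | 4.4% |

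For 10 sites, √1.662 = 1.289. Then 2.804/1.289 − 1.960 = 0.215, which gives 58.5%, and 1.960/1.289 = 1.520, which gives an error of 6.4%. At ICC 0.02 with 10 sites, D is 2.32, power at the 41.3% limit is 45% and the error is 9.9%. These figures use a z reference. With t on 8 degrees of freedom, the 10-site, ICC 0.01 case at the 41.3% limit falls to about 48%.

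**Direction of the error.** Beta-binomial simulation of a site-level exposure analysed by patient (4, 8 or 12 sites, ICC 0.005 to 0.05) gave one-sided error from 0.042 to 0.266. It was above 0.025 in every setting.

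**Whether the planned site handling protects.** If each site has one protocol, a site grouping variable is aliased with protocol. Collapsing returns to the independent-patient test. A triviality check does not restore 0.025. In a simulation at the 41.3% limit (10 equal sites, ICC 0.01, 5% heterogeneity test), about two thirds of runs were collapsed. The error among those was about 5% to 7%, depending on whether heterogeneity was tested across all sites or within groups. The robust errors under Missing Data are there for non-normality, and the fallback's Greenwood errors also treat patients as independent.

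**The case against.** The strongest reply is that the protocol does not describe a between-site comparison. Section 4.1 can be read as saying that every registry site uses the pathway, with no control site at all. A reader might infer from site-level adoption that site and protocol are aliased and that the study therefore has about half its stated power. The document does not support that step, because the control source is simply not given. If both protocols are seen at the same sites, the loss is smaller. This objection stands, and it makes the size of the loss conditional.

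Three further points have weight:
- The sentence in 4.4.1 is general. It can be right for exposures that vary within site, and it calls errors in either direction invalid. It would go too far to say that the plan pools because it thinks pooling is safe.
- The losses at the 41.3% limit overstate those at the 1.2 margin, where 20 sites at ICC 0.01 still give 86%.
- The choice of standard errors is often left to an SAP, which is not shown here.

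None of these supplies the missing independence justification or makes the sentence right for a site-level exposure. Nor is there an arithmetic error, since 672 and 80% both reproduce.

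**Conclusion.** The point holds in conditional form. The 80% at 672 rests on an unstated assumption of independent patients, which sits badly with section 4.4.1's own warning and with site adoption in section 4.1. The stated direction of the error is wrong for an exposure set at site level.

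The direction of the consequence is certain for any positive ICC when the groups consist of different sites. Its size is not, because site number, ICC, equal site sizes and 1:1 allocation are all assumed. The calculations illustrate the risk; they do not estimate the study's actual power.

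**What to change.** 1. State first where the control patients come from, how many sites there are, and whether protocol varies within or between sites.
2. Correct the sentence in 4.4.1: patient-level analysis inflates type I error for a site-level exposure, and deflation can arise only for exposures that vary within site.
3. Restate the power at 672 as conditional on independence, with a design-effect range over site number and ICC. Compute it for the margin and reference distribution that the analysis will actually use.
4. If groups differ by site, replace collapsing after a triviality check with site-clustered standard errors and a small-sample t reference. If both protocols occur within sites, include site as a fixed effect.

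The cost is protocol wording, a less favourable stated power and possibly a wider interval. No additional patients are required.
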